### 5.1.1.5 Site Pooling

No site pooling will be done. All analyses will also be presented by investigational site. No inferential statistics will be presented for by site analyses.

## 5.1.2 Demographics

### 5.1.2.1 Analysis Populations

The distribution of subjects within the analysis populations will be summarized as follows:

**Table 5-4 Analysis Population**

Endpoint	Description	Timing	Methodology
All Screened	List of all screened	Screening and Baseline screening	Listing
mITT, PP and Safety populations	Distribution in total and by treatment group	After randomization	Categorical counts

### 5.1.2.2 Subject Disposition

Subject disposition encompasses the distribution of subjects who enter, complete, and discontinue during each specified analysis period, along with eCRF-reported discontinuation reasons from each respective analysis period. Subject disposition will be summarized as follows:

**Table 5-5 Subject Disposition Summaries**

Endpoint	Description	Timing	Methodology
Study disposition	Distribution in the randomized subjects in total and by treatment group	Month 3, final	Categorical descriptives

### 5.1.2.3 Protocol Deviations

Protocol deviations will be defined in a separate document, including significance classification. Protocol deviations will be presented as follows:

**Table 5-6 Protocol Deviation Summary**

Endpoint	Description	Timing	Methodology
Significant protocol deviations	Number (%) of subjects with significant protocol deviations	During study period	Categorical counts

### 5.1.2.4 Demographics

Demographics will be summarized for mITT population in total and by treatment group as follows:

**Table 5-7 Demographic Summaries**

Endpoint	Description	Timing	Methodology
Age	Age (years) relative to informed consent date	Informed consent	Continuous descriptives
Sex	
 
• Race               
 
○ Male
 
○ Female
 
 
 
• Race               
 
○ Asian
 
 
 
• Ethnicity               
 
○ Chinese
 
 
 
	Screening	Categorical counts

### 5.1.2.5 Baseline Characteristics

Baseline characteristics will be summarized in total and by treatment group for the mITT populations as follows:

**Table 5-8 Baseline Characteristics Summaries**

Endpoint	Description	Timing	Methodology
LFS score as assessed by EI	Number (%) of subjects in each category (Minimal, Mild, Moderate, Marked, Very Marked)	Screening	Categorical descriptives

LFS score as assessed by Subject	Number (%) of subjects in each category (Minimal, Mild, Moderate, Marked, Very Marked)	Randomization	Categorical descriptives
Fitzpatrick skin phototype	Number (%) of subjects in each category (I, II, III, IV, V, VI, as well as I/II, III/IV, V/VI)	Screening	Categorical descriptives
Exposure to Sunlight (hrs per day)	Exposure to Sunlight (hrs per day)	Screening	Continuous descriptives
Smoking status	Number (%) of subjects in each category, current, former, and never smoke	Screening	Categorical counts
Duration of smoking (in years)	Duration of smoking (in years)	Screening	Continuous descriptives

### 5.1.2.6 Medical History

Medical history, encompassing abnormalities and surgeries reported as occurring before the Screening Visit, will be coded using the Medical Dictionary for Regulatory Activities (MedDRA), version 18.1 or newer. Unique subjects who report medical history events will be presented as subject listing for the Safety Population.

**Table 5-9 Medical History**

Endpoint	Description	Timing	Methodology
Abnormalities and surgeries	Abnormalities and surgeries occurring before the Screening Visit	Screening	Listing

### 5.1.2.7 Prior and Concomitant Medications

Medications will be coded using the World Health Organization (WHO) Drug Dictionary, version March 2014 or newer. Unique subjects who reported medications (Anatomical Therapeutic Chemical (ATC) 4 class and PT) will be presented as subject listing for the Safety Population.

**Table 5-10 Medication**

Endpoint	Description	Timing	Methodology	
Treatment Group	Prior medications	Medications taken before the study treatment regardless of medication end date	Screening	Listing
	Concomitant medications during UCP	Medications taken on or after the study treatment and before Safety Day 91 (at month 3), regardless of medication start date or end date (For treatment group, concomitant medications during UCP consist a subset of concomitant medications during TP.)	UCP	Listing
	Concomitant medications during TP	Medications taken on or after the study treatment regardless of medication start date	TP	Listing
Control Group	Prior medications	Medications taken before randomization regardless of medication end date	Screening	Listing
	Concomitant	Medications taken after randomization and before	UCP	Listing

Endpoint	Description	Timing	Methodology
medications during UCP	optional treatment (at month 3), regardless of medication start date or end date		
Concomitant medications during TP	Medications taken on or after the study treatment regardless of medication start date	TP	Listing

### 5.1.2.8 Exposure to Study Treatment

Treatment exposure related variable will be summarized for safety population by treatment group (treatment group and treated control group), treatment (combined initial and touch-up, initial, touch-up), and treatment area as in Table 5-11. For treated control group, data after receiving initial treatment at Month 3 are included.

**Table 5-11 Exposure to Study Treatment**

Endpoint	Description	Timing	Methodology
Volume injected 
 
• Total
 
• Upper Lip
 
• Lower Lip
 
 Philtral Columns	Summarize by treatment group, treatment, and treatment area	Initial, Touch-up	Continuous descriptives
Treatment sites 
 
• Total
 
• Upper Lip               
 
○ Vermilion body
 
○ Vermilion border
 
 
 
• Lower Lip               
 
○ Vermilion body
 
○ Vermilion border
 
 
 
• Philtral Columns
 
	Summarize by treatment group, treatment, and treatment area	Initial, Touch-up	Categorical counts

### 5.1.2.9 Administration of Study Treatment

Variables related to administration of treatment will be summarized for safety population by treatment group (treatment group and treated control group), treatment (initial, touch-up), and treatment area as in Table 5-12. For treated control group, data after receiving initial treatment at Month 3 are included.

**Table 5-12 Administration of Study Treatment**

Endpoint	Description	Timing	Methodology
Pretreatment Anesthesia 
 
• Pretreatment Anesthesia type
 
	Ice, Topical, Injectable, Other	Initial, Touch-up	Categorical counts
Pretreatment Anesthesia duration (minutes) 
 
• Pretreatment Anesthesia duration
 
	Anesthesia duration is computed as injection time minus start of anesthesia administration time. Summarize by treatment group, treatment, and anesthesia type.	Initial, Touch-up	Continuous descriptives
Treatment administration 
 
• Injection technique
 
• Planes of injection
 
• Needle gauge length
 
	Summarize by treatment group, treatment (initial or touch-up), and treatment area	Initial, Touch-up	Categorical counts

Endpoint	Description	Timing	Methodology
Pretreatment Anesthesia 
 
Pretreatment Anesthesia type
 
	Ice, Topical, Injectable, Other	Initial, Touch-up	Categorical counts
Pretreatment Anesthesia duration (minutes) 
 
Pretreatment Anesthesia duration
 
	Anesthesia duration is computed as injection time minus start of anesthesia administration time. Summarize by treatment group, treatment, and anesthesia type.	Initial, Touch-up	Continuous descriptives

 
Massage used
 
Device/Needle problem or malfunction
 
			
Characteristics of the product 
 
Injection ease
 
Product moldability
 
	Summarize by treatment group, treatment (initial or touch-up), and treatment area	Initial, Touch-up	Categorical counts

### 5.1.3 Effectiveness Analyses

All effectiveness analyses will be based on the mITT Population.

The following effectiveness assessments are defined as:

**Table 5-13 Effectiveness Assessments**

Assessment	Description
Lip fullness	Assessed by EI and subject based on the overall lip fullness using the 5-point LFS. (Vey Marked, Marked, Moderate, Mild, Minimal)
Overall lip volume	The volume of the overall lips as measured from 3D images.
Lip surface area	The lip surface area as measured from 3D images.

Baseline assessments for applicable effectiveness endpoints are defined as follows:

**Table 5-14 Effectiveness Endpoint Baseline Definitions**

Endpoint	Description	Timing

 
Overall Lip fullness
 
Overall lip volume
 
Lip surface area
 
Philtral column definition
 
	Baseline refers to the last evaluation prior to initial treatment for treatment group, and prior to randomization for control group	Screening/ Randomization

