8.3 Hypothesis and Methods of Analysis

In general, descriptive statistics will be presented. Categorical variables will be summarized with frequency and percentage. Continuous variables will be summarized by number of subjects, mean, median, standard deviation, minimum, and maximum. Where appropriate, 2-sided 95% confidence intervals (CIs) for mean or proportion will be provided as part of the descriptive summary.

Unless otherwise noted, during posttreatment follow-up visits (for both the VOLBELLA with Lidocaine group and the no-treatment control group), baseline refers to the last evaluation prior to initial treatment; during the no-treatment period (for the no-treatment control group), baseline refers to the last evaluation prior to the month 1 visit.

No imputation for missing data will be performed. However, sensitivity analyses for the primary endpoint will be performed using applicable missing imputations to assess the potential effect of missing data.

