**Table 6-3 Effectiveness Analysis Visit Definitions for Control Group during Control Period**

Analysis Visit	Target Day of the Visit	Analysis Visit Window
Screening a	N/A	Screening visit
Baseline	Day 1	Randomization visit
Month 1	Day 31	Days [2, 61]
Month 3	Day 91	From Day 62 to study exit day if the subject didn't receive optional treatment, or to the day of optional treatment if the subject received optional treatment  The assessments before the optional treatment on that day will be accounted for Month 3 visit.

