**Table 6-4 Effectiveness Analysis Visit Definitions for Control Group during Treatment Period**

Analysis Visit	Target Day of the Visit	Analysis Visit Window
Baseline	N/A	Randomization visit
Initial treatment a	N/A	N/A
Touch-up treatment b	Day 30 After Initial Treatment	Day 30 after initial treatment visit
Last treatment c	Day 1	Day 1
Month 1	Day 31	Days [2, 61]

Month 3	Day 91	Days [62, 136]
Month 6	Day 181	>=Day 137

aInitial treatment is at Month 3 visit.

bNot all subjects will receive touch-up treatment.

cInitial treatment if touch-up is not performed, otherwise touch-up treatment.

If there are multiple visits occurring within a single visit window with relevant data, the visit closest to the target day listed above will be used in the analysis of the corresponding visit windows regardless of scheduled or unscheduled visit. If two visits are equal distant to the target day and are the same type of visit, then the later visit will be used.

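### SAP Table 6-4 gives treated controls a randomization baseline for the treatment period, in conflict with protocol 8.3, and Table 5-14 has no separate rule for that period

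*SAP*

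**What the plan says.** Protocol 8.3 defines baseline by period and names the control group in both rules. For posttreatment follow-up visits the rule reads: "for both the VOLBELLA with Lidocaine group and the no-treatment control group), baseline refers to the last evaluation prior to initial treatment". A separate rule covers the control group's no-treatment period and uses the last evaluation before the month 1 visit. The paragraph opens with a clause allowing exceptions noted elsewhere.

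SAP Table 5-14, the table of baseline definitions for effectiveness endpoints, says: "Baseline refers to the last evaluation prior to initial treatment for treatment group, and prior to randomization for control group". Its timing column refers to screening and randomization. It has no second line for controls once they have had the optional treatment.

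SAP Table 6-4 is titled "Effectiveness Analysis Visit Definitions for Control Group during Treatment Period". Its baseline row reads "Randomization visit", and footnote a says "Initial treatment is at Month 3 visit". The row for initial treatment has no target day and no window.

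SAP 5.1 says that effectiveness data are collected after controls are treated, and defines a treated period covering both groups. SAP 5.3.2, the section for changes to analyses before database lock, lists one item, a dropped cross table of responder ratings. It does not mention baseline.

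**The concern.** For the same subjects in the same period, the protocol and the SAP name different starting points for change from baseline. Under the protocol, a treated control's posttreatment change starts just before the first injection, as it does for the treatment group. Under the SAP wording it starts at randomization, before the untreated months.

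Two things are at stake. Any real change in the lips, or drift in the ratings, during the untreated period would be counted as posttreatment change in treated controls. The two groups' treated-period results would also be measured from different points relative to injection, so showing them side by side or combining them would mix two definitions. A programmer working from the visible SAP tables has no route to the protocol's baseline for these subjects.

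**Working it through.** **The plan's own figure.** The documents give no figure for the baseline gap. The nearest is the power of the primary test, stated as above 96% (protocol 8.5). Exact enumeration of the two-sided Fisher test with 111 and 37 subjects and rates of 79.0% and 44.1% gives 96.7%, so the claim reproduces. None of its inputs depends on the treated-period baseline.

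**Inputs for the gap.**
- Controls before treatment: Day 1 is the randomization date (SAP Tables 6-1 and 6-3).
- Control-period Month 3: target Day 91. The window runs "From Day 62 to study exit day if the subject" is not treated, "or to the day of optional treatment if the subject received optional treatment" (Table 6-3). It opens on Day 62 and has no stated last day.
- Optional treatment: at the Month 3 visit (Table 6-4, footnote a).
- Touch-up: 30 days after initial treatment (Tables 6-2 and 6-4).
- Treated-period Month 3: target Day 91 counted from the last treatment as Day 1, so 91 − 1 = 90 days later (Tables 6-1, 6-2 and 6-4).
- Assumption: the last pre-treatment evaluation is made on the day of injection.

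**Gap between the two candidate baselines for a treated control** = day of optional treatment − 1.
- At target: 91 − 1 = 90 days.
- Earliest day in the window: 62 − 1 = 61 days.
- Latest: not bounded by Table 6-3.

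**Time from baseline to treated-period Month 3** = gap + touch-up delay (0 or 30) + 90.

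| Group and baseline | No touch-up | With touch-up |
|---|---|---|
| Treatment group | 0 + 0 + 90 = 90 days | 0 + 30 + 90 = 120 days |
| Treated controls, protocol 8.3 | 0 + 0 + 90 = 90 days | 0 + 30 + 90 = 120 days |
| Treated controls, SAP wording, at target | 90 + 0 + 90 = 180 days | 90 + 30 + 90 = 210 days |
| Treated controls, SAP wording, earliest | 61 + 0 + 90 = 151 days | 61 + 30 + 90 = 181 days |

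These are calendar intervals. They show how much untreated time enters the comparison, not how far any result would move.

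**Which analyses are reached.** SAP 5.1.3.1 and 5.1.3.2 base the primary and listed secondary analyses on the untreated control period. There the randomization baseline for controls is not in dispute. Only treated-period effectiveness summaries for controls could be affected. Those tables are not visible: SAP Table 5-23 refers to a Table 5-17 that falls in redacted text.

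**The case against.** Several counter-arguments have weight.

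First, a reader might infer that Table 5-14 itself prescribes a randomization baseline after treatment. It does not say so. Its timing column and its place just before analyses of the untreated control period allow it to be read as a control-period rule only. That stands: the explicit conflict is in Table 6-4, and Table 5-14 contributes by offering nothing else.

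Second, Table 6-4 assigns visits to windows, and its baseline row may only attach a label to a visit without saying what is subtracted. This weakens the point but does not remove it. The table covers only treated controls, and no other visible table supplies a different baseline for them.

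Third, the protocol's rule allows exceptions, and the protocol leaves detailed specification to the SAP. A study-entry baseline for a delayed-treatment arm could be deliberate. The SAP may depart, but it gives no visible reason, and 5.3.2 does not mention baseline. It would be wrong to read 5.3.2 as declaring that nothing changed: it declares one change, unrelated to this.

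Fourth, a local baseline rule may sit in the redacted treated-period tables. This cannot be excluded. Table 6-4 as it stands would still disagree with protocol 8.3.

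Fifth, the absence of an upper limit applies to the Table 6-3 analysis window only. The protocol describes a three-month untreated period, and the visit schedule that might limit timing is not visible.

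**Conclusion.** The conflict is real and minor. Protocol 8.3 and SAP Table 6-4 give different baselines for treated controls at posttreatment visits, and no visible text reconciles them. Confidence is high in that textual conflict and does not extend to its consequences.

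Under the SAP wording the starting point moves back nominally 90 days from injection, and at least 61 days if the optional treatment falls within the Month 3 analysis window. This rests on the target days and windows in SAP Tables 6-1 to 6-4 and on a pre-treatment evaluation on the injection day.

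Two stronger conclusions might be inferred, and the documents support neither. One is that the main comparison is compromised. It is not: the primary and listed secondary analyses use the untreated control period, and the power is untouched. The other is that treated controls' responder rates would be inflated, because the sample size allows for up to 44.1% of untreated controls to respond by month 3. That figure is a planning value taken from a study of another product. Turning it into an inflation would also require assuming how early gains relate to later response and that they persist. Untreated ratings could drift either way, so neither the size nor the direction of any effect can be derived.

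**What to change.** In SAP Table 6-4, set the treatment-period baseline for controls to the last evaluation before the initial optional treatment, as in protocol 8.3. In Table 5-14, give controls two lines: the randomization baseline for the control period and the pre-treatment baseline for the treatment period. If a randomization baseline is intended after treatment, state that in SAP 5.3.2 with the reason. Either should be settled before database lock.

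The cost is wording in two tables and the matching programming. No new data are needed. The protocol synopsis requires lip fullness ratings before initial treatment and 3D imaging before each treatment, and puts treated controls on the same schedule. Table 6-3 already uses the pre-injection assessments: "The assessments before the optional treatment on that day will be accounted for Month 3 visit". The same assessment can close the control period and serve as baseline for the treatment period.

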STUDY DESIGN: 
This is a prospective, multicenter, randomized, no-treatment-controlled study to evaluate the safety and effectiveness of VOLBELLA with Lidocaine for lip enhancement in a Chinese population.
 
Subjects will be randomized at a 3:1 ratio either to have treatment with VOLBELLA with Lidocaine at the outset of the study (VOLBELLA with Lidocaine group, also referred to as the treatment group) or to have treatment delayed by 3 months (no-treatment control group). Treatment and safety assessments of a subject throughout the study will be performed by the same Treating Investigator (maximum 2 Treating Investigators per site), and effectiveness assessments will be performed by the same Evaluating Investigator. The Evaluating Investigator will remain blinded to treatment assignments throughout the duration of the study. Subjects randomized to the treatment group should undergo treatment on the same day as randomization. If initial treatment does not occur on the randomization day for subjects in the treatment group, it must occur within 30 days after screening. Subjects randomized to the no-treatment control group will attend study visits at months 1 and 3 of the no-treatment control period at which they will undergo effectiveness measures also performed at randomization. These measures include the Evaluating Investigator's assessment of the subject's lip fullness using the 5-point Lip Fullness Scale (LFS; 5 points: Minimal, Mild, Moderate, Marked, and Very Marked) and facial 3-dimensional (3D) imaging. [REDACTED]
 
[REDACTED]
 
[REDACTED] In addition, vital signs will be collected. After the completion of the control period, subjects randomized to the no-treatment control group will receive optional treatment for lip enhancement and follow the same schedule of visits and procedures in the treatment period as described below and in Table 1 for subjects randomized to the treatment group.
 
On the initial treatment day, the trained Treating Investigator will inject VOLBELLA with Lidocaine into the lips, as needed for lip enhancement. Allowable treatment areas are the vermilion body, vermilion border (including the Cupid's bow), and philtral columns. Prior to initial treatment, the Evaluating Investigator and the subject will rate the subject's lip fullness by using the LFS, and the Evaluating Investigator will rate the subject's philtral column definition by using a 5-point scale (Not Defined, Barely Defined, Somewhat Defined, Well-defined, and Very Well-defined). On day 30 after initial treatment, the Evaluating Investigator will again rate the subject's lip fullness and philtral column definition. Subjects may undergo an optional touch-up treatment at the day 30 visit after initial treatment, if the Treating Investigator assesses that optimal correction was not achieved. At each treatment visit, the subject will rate procedural pain on an 11-point scale immediately after receiving the injections, and the Treating Investigator will assess the ease of injection and the product moldability. Subjects will complete a safety diary for 30 days after each treatment and will complete a safety follow-up telephone call at 3 days after each treatment. Before treatment on each treatment day, the subject will undergo facial 3D imaging, which will also be performed 30 days after treatment.
 
Routine follow-up visits for safety and effectiveness will occur at 1, 3, and 6 months after the last treatment for both groups. At these visits, facial 3D imaging will be performed, [REDACTED]

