**Table 5-1 Analysis Populations**

Population	Definition	Study Treatment
Modified Intent-to-Treat (mITT) population	
 
All subjects who are randomized to study treatment (treatment group) and receive at least 1 study device treatment and have baseline and at least 1 post-treatment assessment of the primary variable
 
All subjects who are randomized to the no-treatment control group and have baseline and at least 1 follow-up assessment of the primary variable
 
	As treated
Per-protocol (PP) population	All mITT subjects who have baseline LFS score of Minimal, Mild, or Moderate, have Month 3 LFS assessments, and do not have any significant protocol deviations affecting the primary effectiveness endpoint	As treated
Safety population	
 
All subjects randomized to the treatment (treatment group) who receive at least 1 study treatment
 
All subjects randomized to the control group
 
	As treated

Subjects will be analyzed as treated. All effectiveness analyses will be performed using the mITT population. Additional sensitivity analyses for the primary effectiveness analysis will also be performed using PP population. All safety analyses will be performed using the safety population.

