**Table 6-2 Effectiveness Analysis Visit Definitions for Treatment Group**

Analysis Visit	Target Day of the Visit	Analysis Visit Window
Screening a	N/A	Screening visit
Baseline	N/A	Randomization/Initial treatment visit
Touch-up treatment b	Day 30 After Initial Treatment	Day 30 after initial treatment visit
Last treatment c	Day 1	Day 1
Month 1	Day 31	Days [2, 61]
Month 3	Day 91	Days [62, 136]
Month 6	Day 181	>=Day 137

a Subjects may have screening and randomization on the same day. In such cases, only randomization visit is relevant.

b Not all subjects will receive touch-up treatment.

c Initial treatment if touch-up is not performed, otherwise touch-up treatment

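### The SAP sets the primary LFS baseline by a different rule in each arm, so VOLBELLA subjects treated after the randomization day can have a post-randomization baseline with no counterpart in controls

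*SAP*

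**What the plan says.** **SAP baseline rule.** Table 5-14: "Baseline refers to the last evaluation prior to initial treatment for treatment group, and prior to randomization for control group". The visit windows repeat the difference. Table 6-2 gives the VOLBELLA baseline as "Randomization/Initial treatment visit"; Table 6-3 gives the control baseline as "Randomization visit".

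**Timing of treatment.** Protocol Synopsis, Study Design: "Subjects randomized to the treatment group should undergo treatment on the same day as randomization". It then allows for delay: "If initial treatment does not occur on the randomization day for subjects in the treatment group, it must occur within 30 days after screening". SAP Section 4.1.1 carries the same allowance.

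**Rating before injection.** The synopsis paragraph on the initial treatment day says: "Prior to initial treatment, the Evaluating Investigator and the subject will rate" lip fullness.

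**Stratification.** Protocol Section 4.5 stratifies by the Evaluating Investigator's LFS at the randomization visit, in three levels from Minimal to Moderate.

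**Protocol baseline rule.** Section 8.3 uses the last evaluation before initial treatment for posttreatment visits. For the control group's untreated period, "baseline refers to the last evaluation prior to the month 1 visit". That is not the SAP's control rule, and SAP Section 5.3.2 does not list a change.

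**Per-protocol (PP) population.** SAP Table 5-1 admits "All mITT subjects who have baseline LFS score of Minimal, Mild, or Moderate", with further conditions.

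**The concern.** The primary outcome is a gain of at least one grade from baseline, so whichever rating counts as baseline helps to decide who is a responder. The plan allows for up to 44.1% responders among untreated subjects. If much of that is movement in the rating itself, changing the baseline rating changes the responder rate.

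A control's baseline is fixed before assignment. A deferred VOLBELLA subject's baseline may be set after assignment, at a visit that controls do not have. This could act in two directions. The randomization-visit rating is limited to Moderate or below and so carries some regression to the mean, which a fresh rating lacks; dropping it would lower the VOLBELLA responder rate. On the other hand, if the extra visit hinted at allocation, a low re-rating would raise that rate.

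The PP population has a one-sided version of the same problem. A re-rating above Moderate removes a VOLBELLA subject, while a control's stratification rating cannot exceed Moderate.

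**Working it through.** **1. Which rating is used.**

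| Subject | Baseline under SAP Table 5-14 | Same as stratification rating? |
|---|---|---|
| Control | Randomization visit | Yes |
| VOLBELLA, treated on randomization day | Randomization visit | Yes |
| VOLBELLA, treated later and re-rated | Treatment visit, after randomization | Not necessarily |
| VOLBELLA, treated later and not re-rated | Randomization visit | Yes |

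Only the third row departs from the rest.

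**2. The plan's own power figure.** Inputs from Protocol Section 8.5: 111 and 37 evaluable subjects, responder rates of 79.0% and 44.1%, two-sided Fisher's exact test at 5%. Enumerating all outcomes with binomial weights gives 96.7%, which agrees with the stated figure of more than 96%. The planned difference is 79.0 − 44.1 = 34.9 points (SAP Table 5-24 prints 34.1%).

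**3. Shift from re-rating alone.** Let f be the share of VOLBELLA subjects deferred and d the change in their responder probability. The arm-level shift is f × d. Neither value is in the documents.

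To get d, I assumed a true lip-fullness score (mean 1.0-1.5, SD 0.6-1.0) plus independent rating noise, rounded to 0-4, with entry if the enrolment rating is 2 or less. Untreated drift was 0 to 0.4 grade. Noise was set so that 44.1% of untreated subjects respond, and the treatment effect so that 79% of treated subjects respond against the enrolment rating. Measured against an independent re-rating instead:

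- the responder rate in deferred subjects is 66-78%, so d runs from 78 − 79 = −1 to 66 − 79 = −13 points;
- 2-22% are re-rated above Moderate.

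With f assumed at 10-25%:

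- smallest shift: 0.10 × (−1) = −0.1 point;
- largest shift: 0.25 × (−13) = −3.25, about −3 points;
- power at 76.0% against 44.1%: 92.9%;
- share of the VOLBELLA arm leaving PP: 0.10 × 2% = 0.2% to 0.25 × 22% = 5.5%.

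**4. Either direction.** Because rater expectation could push the other way, here are round assumed values with the same exact test. The last column is the chance of a false superiority finding if both true rates are 44.1% and the shift is added to VOLBELLA (nominal 2.5% per side).

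| f | d (points) | Shift (points) | Power | False superiority |
|---|---|---|---|---|
| 0 | any | 0 | 96.7% | 1.9% |
| 10% | −20 | −2 | 94.4% | 1.1% |
| 10% | +20 | +2 | 98.3% | 3.1% |
| 25% | −20 | −5 | 89.0% | 0.5% |
| 25% | +20 | +5 | 99.4% | 5.9% |

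The last two rows need a quarter of the arm deferred and a 20-point effect in each deferred group, which is extreme.

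**The case against.** **A second rating is not certain.** The protocol sentence on rating before treatment would be met by a rating at the randomization visit. The Timing column of Table 5-14 names only screening and randomization, and Table 5-8 places the Evaluating Investigator's baseline LFS at screening. The Table 6-2 entry can be read as one combined visit. The visit schedule that would settle this is blacked out. This stands in part: because the sentence sits in the paragraph on the treatment day, a re-rating is likely but not established. Without one, the two rules coincide.

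**Deferral is the exception.** Same-day treatment is the default. The 30-day limit runs from screening, and randomization may itself use part of it (Protocol Section 10.1.3). This stands, and it limits the size.

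**Blinding.** A reader might infer that the extra visit reveals allocation to the rater. The documents do not support that. Protocol Section 4.3.3 keeps the Evaluating Investigator blinded, away from the injections and without access to treatment records. Screening and randomization ratings can also fall on separate days in either arm, so a repeat rating before treatment is not in itself unique to VOLBELLA. An extra visit could hint at allocation, no more.

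**Regression to the mean.** The contrast is less clean than the simulation makes it. Where screening and randomization are separate visits, the stratification rating is already a second rating in both arms. The same Evaluating Investigator rates each subject throughout, so correlated ratings would shrink the gap. The 44.1% is an upper value from a US study of another product.

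**The VOLBELLA rule follows the protocol.** This stands. Against Protocol Section 8.3, the SAP departs on the control side, so any fix must reconcile the two documents.

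**Conclusion.** The arm-specific baseline rule is real and sits in the operative SAP text for the primary endpoint. It opens the way to a post-randomization baseline in one arm only, and only for VOLBELLA subjects treated after the randomization day.

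Under the assumed 10-25% deferral and the rating model above, the shift is about 0.1 to 3 points against a planned 34.9. Those figures assume that every deferred subject is re-rated and that rating errors are independent. The net direction is uncertain: regression to the mean works against VOLBELLA, and a hint of allocation could work for it.

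A reader might infer that the primary comparison is biased towards VOLBELLA or cannot be relied on. The documents do not support that: the deferral rate is unknown, the rater is blinded, and the plausible shift is far smaller than the planned difference. The PP asymmetry touches a sensitivity analysis only. This is a cheap improvement and a needed reconciliation of texts. It gives no reason to doubt the design, and the planned power and sample size do not change.

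**What to change.** 1. In SAP Tables 5-14 and 6-2, define baseline for the month 3 randomized comparison, in both arms, as the Evaluating Investigator's LFS at the randomization visit, recorded before assignment is obtained from the IVRS/IWRS.
2. Apply the PP baseline condition in Table 5-1 to that same rating.
3. Report the number of VOLBELLA subjects treated after the randomization day, and repeat the primary analysis with the last pre-treatment rating as baseline, as a sensitivity analysis.
4. Reconcile Table 5-14 with Protocol Section 8.3, whose rules differ, and list the change in SAP Section 5.3.2. Align the Timing entries in Tables 5-14 and 5-8.

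**Cost.** No new data are needed, because the rating is already taken for stratification. The work is SAP wording, one extra sensitivity table and a recorded departure from Protocol Section 8.3. The downside is that a deferred subject's baseline can be up to 30 days older than the injection; the sensitivity analysis in item 3 shows whether that matters.
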